3.2.4 Duration of response (DoR)

DoR (per RECIST 1.1, using Investigator assessment) will be calculated for all patients with a confirmed overall response of CR or PR, and will be defined as the time from the date of first documented response (which is subsequently confirmed) until the first date of documented progression or death in the absence of disease progression (i.e. date of PFS event or censoring – date of first response + 1). The end of response should coincide with the date of progression or death from any cause used for the (RECIST 1.1) PFS endpoint.

The time of the initial response will be defined as the latest of the dates contributing towards the first visit response of PR or CR that was subsequently confirmed. If a patient does not progress following a response, then their DoR will be censored at the PFS censoring time.

DoR will not be defined for those patients who do not have documented response.

3.2.5 Best objective response (BoR)

BoR is calculated based on the overall visit responses from each (RECIST 1.1, using Investigator assessment) assessment. It is the best response a patient has had during their time in the study, but prior to starting any subsequent cancer therapy and up until (RECIST 1.1) progression or the last evaluable assessment in the absence of (RECIST 1.1) progression.

Categorization of BoR for solid tumors will be based on RECIST 1.1 using the following response categories: CR, PR, SD, PD, and NE.

CR or PR must be confirmed (confirmed is defined as 2 consecutive assessments with the same outcome, not less than 4 weeks apart). BoR will be determined programmatically (based on RECIST 1.1) using all Investigator assessments up until the first progression event. For patients whose progression event is death, BoR will be calculated based upon all evaluable (RECIST 1.1) assessments prior to death.

For patients who die with no evaluable (RECIST 1.1) assessments, if the death occurs ≤ 119 days (i.e. 2×8 weeks + 7 days) after first dose of study treatment, then BoR will be assigned to the progression (PD) category. For patients who die with no evaluable (RECIST 1.1) assessments, if the death occurs > 119 days (i.e. 2×8 weeks + 7 days) after the date of first dose of study treatment, then BoR will be assigned to the NE category.

Progression events that have been censored due to them being > 119 days after the last evaluable assessment will not contribute to the BoR derivation.

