9.4.1.2 Primary endpoint: Objective response rate

Objective response rate (per RECIST 1.1 or INRC, using Investigator assessments) is defined as the percentage of patients with at least 1 visit response of CR or PR that is subsequently confirmed on another scan not less than 4 weeks after visit observed response. Data obtained up until progression, or the last evaluable assessment in the absence of progression, will be included in the assessment of ORR. Patients who go off treatment without progression, receive a subsequent therapy, and then respond will not be included as responders in the ORR.

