9.4.1.6 Best objective response

Best objective response (BoR) is calculated based on the overall visit responses from each RECIST 1.1 (or INRC) assessment. It is the best response a patient has had during their time in the study up until RECIST 1.1 (or INRC) progression or the last evaluable assessment in the absence of RECIST 1.1 (or lymphoma criteria or INRC) progression.

Categorization of BoR for solid tumors will be based on RECIST 1.1 ([Appendix E](#)) using the following response categories: CR, PR, SD, PD, and NE.

For NB, the categories will be based on INRC ([Appendix F](#)) and they are CR, PR, minor response (MR), SD, PD, and NE (applicable for the dose-finding phase only).

Complete response or PR must be confirmed. Best objective response will be determined programmatically based on RECIST 1.1 (or lymphoma criteria or INRC) using all Investigator assessments up until the first progression event. For patients whose progression event is death, BoR will be calculated based upon all evaluable RECIST 1.1 (or INRC) assessments prior to death.

For patients who die with no evaluable RECIST 1.1 (or INRC) assessments, if the death occurs ≤ 119 days (ie, 2×8 weeks + 7 days) after first dose of IP, then BoR will be assigned to the progression (PD) category. For patients who die with no evaluable RECIST 1.1 (or INRC) assessments, if the death occurs > 119 days (ie, 2×8 weeks + 7 days) after the date of first dose of IP, then BoR will be assigned to the NE category.

Progression events that have been censored due to them being > 119 days after the last evaluable assessment will not contribute to the BoR derivation.

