Table 4 Summary outcome variables and analysis sets

Outcome variable	Analysis set
Efficacy Data	
ORR (primary for dose-expansion phase [confirmed responses])	Evaluable for response analysis set (Sensitivity analysis on FAS)
ORR (unconfirmed responses)	(Sensitivity analysis on Evaluable for response analysis set)
PFS, OS, BoR (confirmed responses), APF12, APF18, OS12, OS24	FAS
DoR	Evaluable for response analysis set (restricted to confirmed responders only)
DCR	Evaluable for response analysis set (Sensitivity analysis on FAS)

Table 4 Summary outcome variables and analysis sets

Outcome variable	Analysis set
Demography	FAS
PK data	PK analysis set
ADA data	ADA analysis set
Safety Data	
Exposure	SAS
AEs	SAS
Laboratory measurements	SAS
Vital Signs	SAS
DLTs (primary for dose-finding phase)	DLT evaluable analysis set

AE Adverse event; APF12 / APF18 Proportion of patients alive and progression-free at 12 / 18 months from first dose of study treatment; BoR Best objective response; DCR Disease control rate; DLT Dose-limiting toxicity; DoR Duration of response; FAS Full analysis set; OS Overall survival; ORR Objective response rate; OS12 / OS24 Proportion of patients alive at 12 / 24 months from first dose of study treatment; PFS Progression-free survival; PK Pharmacokinetics; SAS Safety analysis set.

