NA	No TLs are recorded at baseline.

CR Complete response; PD Progressive disease; PR Partial response; SD Stable disease; NA Not applicable; NE Not estimable.

Rounding of TL data

For calculation of PD and PR for TLs percentage changes from baseline and previous minimum should be rounded to one decimal place before assigning a TL response. For example, 19.95% should be rounded to 20.0% but 19.94% should be rounded to 19.9%.

Missing TL data

If all TL measurements are missing then the TL visit response is NE. Overall visit response will also be NE, unless there is a progression of non-TLs or new lesions, in which case the response will be PD.

Lymph nodes

For lymph nodes, if the size reduces to < 10 mm then these are considered non-pathological. However, a size will still be given, and this size should still be used to determine the TL visit response as normal. In the special case where all lymph nodes are < 10 mm and all other TLs

are 0mm then although the sum may be > 0 mm the calculation of TL response should be over-written as a CR.

TL visit responses subsequent to CR

A CR can only be followed by CR, PD or NE. If a CR has occurred, then the following rules at the subsequent visits must be applied:

- Step 1: If all lesions meet the CR criteria (i.e. 0mm or < 10 mm for lymph nodes) then response will be set to CR irrespective of whether the criteria for PD or TL is also met i.e. if a lymph node LD increases by 20% but remains < 10 mm.
- Step 2: If some lesion measurements are missing but all other lesions meet the CR criteria (i.e. 0mm or < 10 mm for lymph nodes) then response will be set to NE irrespective of whether, when referencing the sum of TL diameters, the criteria for PD are also met.
- Step 3: If not all lesions meet the CR criteria and the sum of lesions meets the criteria for PD then response will be set to PD.
- Step 4: If after steps 1 – 3 a response can still not be determined the response will be set to remain as CR.

TL too big to measure

If a TL becomes too big to measure this should be indicated in the database and a size ('x') above which it cannot be accurately measured should be recorded. If using a value of x in the calculation of TL response would not give an overall visit response of PD, then this will be flagged and reviewed by the study team blinded to treatment assignment. It is expected that a visit response of PD will remain in the vast majority of cases.

TL too small to measure

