3.2 Efficacy Variables

3.2.1 Objective response rate (ORR)

ORR (per RECIST 1.1, using Investigator assessments) is defined as the percentage of patients with at least 1 investigator-assessed visit response of CR or PR that is subsequently confirmed on another scan not less than 4 weeks after visit observed response. Data obtained up until progression, or the last evaluable assessment in the absence of progression, will be included in the assessment of ORR. Patients who go off treatment without progression, receive a subsequent therapy, and then respond will not be included as responders in the ORR.

ORR is primary endpoint of dose-expansion phase.

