4.2.2.1 Objective response rate (ORR)

The ORR will be based on the programmatically derived (RECIST 1.1) outcome. The point estimate and 90% confidence interval (CI) (2-sided) of the ORR will be presented for each if the three analysis cohorts. If the cohort is expanded after the initial DRC review, the CI will be calculated using an exact Mid-P method (Porcher and Desseaux 2012). If the cohort is not expanded an exact CI will be presented.

90% Mid-p confidence limits are the values that have a one-sided Mid-p value of 0.05. (A Mid-p value for a one-sided test is obtained by including in the tail only one-half of the probability of the observed sample).

The exact Mid-p confidence limits θ_L (lower limit) and θ_U (upper limit) are those values which satisfy the equations:

$$\sum_{i=0}^n p_i(\theta_L) - \frac{1}{2}p_n(\theta_L) = 0.95$$

$$\sum_{i=0}^n p_i(\theta_U) - \frac{1}{2}p_n(\theta_U) = 0.05$$

This analysis will be performed on the evaluable for response analysis set.

Summaries will be produced that present the number and percentage of patients with a confirmed tumor response (CR/PR).

Sensitivity analyses will be performed for tumor response (CR/PR) on FAS and "unconfirmed CR/PR" on the evaluable for response analysis set.

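### SAP 3.2.5 confirms CR or PR for best objective response by a stricter rule than SAP 3.2.1 uses for ORR, so two outputs on the full analysis set can disagree about who is a confirmed responder

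*SAP*

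**What the plan says.** **ORR.** SAP 3.2.1 counts a patient who has at least one investigator-assessed CR or PR visit "that is subsequently confirmed on another scan not less than 4 weeks after visit observed response". Protocol 9.4.1.2 has the same condition: "subsequently confirmed on another scan not less than 4 weeks after visit observed response". Neither says that the second scan must be the next one, or must show the same category as the first.

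**BoR.** Protocol 9.4.1.6 says "Complete response or PR must be confirmed" and adds no definition. SAP 3.2.5 adds one: "confirmed is defined as 2 consecutive assessments with the same outcome, not less than 4 weeks apart". It lists CR and PR as separate categories, next to SD, PD and NE. SAP section 6, which records departures from the protocol, does not mention this condition.

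**Where the two are reported.** SAP Table 4 bases both on confirmed responses: "ORR (primary for dose-expansion phase [confirmed responses" for ORR and "PFS, OS, BoR (confirmed responses), APF12, APF18, OS12, OS24" for the group containing BoR, which is analysed on the FAS. The primary ORR is on the evaluable for response set, but SAP 4.2.2.1 adds the FAS: "Sensitivity analyses will be performed for tumor response (CR/PR) on FAS". The reader will therefore see a FAS responder count and a FAS BoR table.

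**Related text.** SAP 3.1.1.1 limits what may follow a target-lesion CR: "A CR can only be followed by CR, PD or NE". SAP 3.2.6 builds the disease control rate on a BoR that it labels unconfirmed. SAP 3.2.5 does not say which category an unconfirmed CR or PR receives.

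**The concern.** Most readers will expect CR plus PR in the FAS BoR table to equal the number of responders in the FAS ORR analysis, since Table 4 calls both confirmed. Under the literal text the two can differ. The SAP does not warn of this or say which count to prefer.

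The literal BoR rule also behaves oddly. It accepts a PR that stays a PR, but rejects a PR that deepens to CR on the last evaluable scan. A patient rejected in this way has no stated BoR category, so the programmer would have to choose one. That choice is better made before the response data are seen.

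At stake is the consistency of two descriptive or supportive tables. The primary result is not at stake.

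**Working it through.** **The design, for context.** SAP 1.3 gives 11 + 15 = 26 evaluable SARCOMA patients. The cohort continues at 2 or more responses in 11, and the null is rejected at 5 or more in 26. The limits are a type I error of 0.10 one-sided at ORR 10% and power of at least 85% at ORR 30%.

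P(reject) = sum over x = 2 to 11 of C(11,x) p^x (1-p)^(11-x) × P[Bin(15,p) ≥ 5 - x].

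- p = 0.10: 0.0865, within 0.10.
- p = 0.30: 0.8516, above 0.85.
- Stage 1 stop at p = 0.10: 0.9^11 + 11 × 0.1 × 0.9^10 = 0.3138 + 0.3835 = 0.697.

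The stated design reproduces. It counts responses as SAP 3.2.1 defines them, and BoR does not enter.

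**The two rules side by side.** Each rule is applied literally to overall visit responses before progression, with scans 8 weeks apart and no subsequent therapy.

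| Sequence | ORR responder (3.2.1) | BoR of CR or PR (3.2.5) |
|---|---|---|
| PR-PR-CR | yes | yes (PR) |
| PR-CR-CR | yes | yes (CR) |
| PR-CR, then PD or end of follow-up | yes | no |
| PR-NE-PR | yes | no |
| CR-NE-CR | yes | no |
| PR-SD-PR | yes, on the bare wording | no |

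**Direction.** Any sequence that passes 3.2.5 has two CRs or two PRs at least 4 weeks apart before progression, so it also passes 3.2.1. On confirmation alone, the FAS ORR count can exceed CR + PR in the BoR table but cannot fall below it.

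**Can the patterns occur?** The 3.1.1.1 rule lets a target-lesion CR be followed by PD or NE, so an unrepeated CR after PR is possible. SAP Table 3 requires follow-up for only 3 cycles, to allow a confirmatory scan 4 weeks after the first assessment, so an evaluable patient may have just those two scans. That rule also covers target lesions only. Under Table 8, a target CR with non-target disease that is not evaluable, or persists without progression, is an overall PR, so an overall CR followed by an overall PR is possible too. An NE visit can sit between two responses. SAP 3.2.2 says, for PFS, that an NE visit is not a missed visit, which supports treating it as an intervening assessment.

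**A softer reading.** If *same outcome* means again a response of either kind, PR-CR passes both rules. PR-NE-PR and CR-NE-CR still fail 3.2.5, because the two responses are not consecutive.

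**Size of one patient.** The FAS contains the evaluable set. For a fully enrolled SARCOMA cohort, the plan's ratio of 36 evaluable to 43 dosed gives 26 × 43/36 = 31.1, and 20% non-evaluable gives 26/0.8 = 32.5. One discordant patient is then 1/31 = 3.2 to 1/33 = 3.0 percentage points, and at most 1/26 = 3.8. If the cohort stops at stage 1 it is at most 1/11 = 9.1.

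The documents give no basis for the share of responders with such a pattern, so no probability of a mismatch is offered.

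**The case against.** The strongest reply is that there may be only one rule. SAP 3.2.1 does not spell out what confirms a response, and the parenthesis in 3.2.5 is the only place where the SAP defines the word. A programmer could carry it into ORR, BoR and duration of response alike, and the counts would then agree. That reading is possible. It shows that the text is ambiguous, not that it is settled, and it would import into the primary endpoint a condition that protocol 9.4.1.2 does not contain.

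Second, *same outcome* may mean only that the patient is again in response. This is fair, and it removes the PR-CR case. It leaves a response separated by an NE.

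Third, both documents send response assessment to CSP Appendix E, whose text was not available to check. It may cover part of this, but it would not remove the SAP's own wording.

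Fourth, both definitions are printed, and overall visit responses are listed for the FAS (SAP 4.2.2.5), so a discrepancy could be traced by hand. That stands, and it keeps the point small.

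A reader might go further and infer that the primary ORR or the stage decisions are compromised. The documents do not support that. ORR has its own definition in 3.2.1, and SAP section 5 applies the SAP's derivations to the Data Review Committee's analyses. The 2/11 and 5/26 rules would be touched only if someone counted responders from BoR, and nothing in the plan says to do so.

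**Conclusion.** The inconsistency is real and minor. SAP 3.2.5 sets a condition for confirmed BoR that is stricter on its face than the ORR rule in SAP 3.2.1 and protocol 9.4.1.2. The condition is absent from protocol 9.4.1.6 and is not declared in SAP section 6. Taken literally, it lets the FAS ORR sensitivity analysis show more confirmed responders than the FAS BoR table. The softer reading of *same outcome* narrows the gap but does not close it.

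Each affected patient moves the FAS percentage by about 3 points at full SARCOMA enrolment. How many there would be cannot be derived from the documents. Protocol 9.5.1.4 plans no formal analysis of BoR, and the FAS ORR is a sensitivity analysis. The primary ORR and the 2/11 and 5/26 rules are unaffected, provided 3.2.1 is applied as written. The conclusion rests on the literal text of both sections and on Appendix E containing nothing that overrides it.

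**What to change.** Replace the parenthesis in SAP 3.2.5 with the 3.2.1 rule: a CR or PR visit response is confirmed by a CR or PR on a later scan at least 4 weeks afterwards and before progression, and a PR followed by one unrepeated CR has BoR = PR. State the category for an overall CR followed by an overall PR as well. Every confirmed responder in ORR then has a BoR of CR or PR. Leave the existing text on subsequent anticancer therapy alone.

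If a rule for an intervening NE or SD is added, say openly that it also specifies the primary ORR, because 3.2.1 has no such rule now. Fix it before the data are analysed and check it against CSP Appendix E.

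State which BoR category an unconfirmed CR or PR receives. Give the DCR input in 3.2.6 a different name from the confirmed BoR. Record the clarification in SAP section 6.

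The cost is a few lines of SAP text and one programmed flag, with no new data. At most a few patients would change BoR category.

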3.2.6 Disease control rate (DCR)

DCR at 16 or 24 weeks will be defined as the proportion of patients who achieve a BoR of unconfirmed CR or PR, respectively, or who have SD (without subsequent cancer therapy) for at least 16 weeks – 7 days or 24 weeks - 7 days, respectively, after start of treatment. For NB, MR will be included in the DCR count.

DCR will be determined programmatically (based on RECIST 1.1, using Investigator assessment) from the overall visit response using all data up until the first progression event.

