9.4.1.7 Disease control rate

Disease control rate at 16 or 24 weeks will be defined as the proportion of patients who achieve best response of CR or PR, respectively, or who have SD for at least 16 weeks - 7 days or 24 weeks - 7 days, respectively, after start of treatment.

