9.5.1.3 Disease control rate

For DCR, the point estimate and 90% CI (2-sided) will be presented. The CI will be calculated using an exact Mid-P method.

Sensitivity analysis will be performed for tumor response (CR/PR) on FAS and "unconfirmed CR/PR" on evaluable for response analysis set.

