6 CHANGES OF ANALYSIS FROM PROTOCOL

As there is no current plan to incorporate irRECIST, this has not been referenced in the SAP.

The definition of the evaluable for response analysis set has been updated to align with the definition in the DRC charter.

An additional sensitivity analysis of ORR using unconfirmed responses has been added.

Clarification has been added that the mid-P methodology is applicable only if the cohorts are expanded.

Visit windowing of safety domains will be considered up to end of treatment, rather than up to progression as mentioned in the protocol.

An additional efficacy listing detailing dose-finding cohort overall RECIST response per investigator assessment has been added.

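### SAP 3.2.6 builds disease control rate on unconfirmed responses, against the SAP's own BoR rule and the protocol, without declaring the change

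*SAP*

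**What the plan says.** **SAP 3.2.6 (DCR).** The responder component is "the proportion of patients who achieve a BoR of unconfirmed CR or PR, respectively". The stable-disease component must last "for at least 16 weeks – 7 days or 24 weeks - 7 days, respectively, after start of treatment". DCR is derived "from the overall visit response using all data up until the first progression event".

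**SAP 3.2.5 (best objective response).** "CR or PR must be confirmed (confirmed is defined as 2 consecutive assessments with the same outcome", with the two assessments at least 4 weeks apart. The only categories are CR, PR, SD, PD and NE.

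**Protocol 9.4.1.7 (DCR).** The responder component is "the proportion of patients who achieve best response of CR or PR, respectively"; the word unconfirmed does not appear. Protocol 9.4.1.6, which defines best response, states: "Complete response or PR must be confirmed".

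**Protocol 9.5.1.3 (DCR analysis).** Unconfirmed responses appear only in a sensitivity analysis: "unconfirmed CR/PR' on evaluable for response analysis set".

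**SAP 4.2.2.6 (DCR analysis).** A point estimate and two-sided 90% CI are planned at each time point on the evaluable set. The interval is mid-P if the cohort is expanded and exact otherwise. The only sensitivity analysis is on the FAS.

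**SAP Section 6 (changes from protocol).** The one entry on unconfirmed responses concerns ORR: "An additional sensitivity analysis of ORR using unconfirmed responses has been added". DCR is not mentioned there, although SAP Section 1 undertakes to describe changes from the protocol.

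**The concern.** Within the SAP, a best objective response of unconfirmed PR cannot exist under 3.2.5, so a programmer has to break either 3.2.5 or 3.2.6. Against the protocol, the SAP promotes a sensitivity definition to the main one and drops the confirmed version altogether. Section 6 does not tell the reader this has happened.

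DCR is a listed efficacy endpoint, reported at two time points with its own interval. In cohorts of 10 to 26 patients, one patient moves the rate visibly. The report could also show a DCR that does not reconcile with the confirmed BoR table beside it.

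**Working it through.** The documents give no DCR target, power or expected rate, so there is no planned figure to reproduce. The check compares the definitions on one patient and then sizes the effect.

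**Inputs**
- Scans every 8 weeks, ±1 week, counted from first dose (protocol Table 2, SAP 3.1).
- First dose is study day 1 (SAP 4.1).
- Evaluable patients: SARCOMA 11 in stage 1 and 26 in total; STO 10 (SAP 1.3).
- Stable-disease thresholds: 16 × 7 − 7 = 105 days and 24 × 7 − 7 = 161 days (SAP 3.2.6, protocol 9.4.1.7).

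**Example patient.** PR at the week-8 scan, no intermediate confirmatory scan, PD at the week-16 scan. The nominal PD day is 16 × 7 + 1 = 113, or 106 to 120 with the window.

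| | SAP 3.2.6 | Protocol 9.4.1.6 and 9.4.1.7 |
|---|---|---|
| Does the week-8 PR count? | Yes; it precedes progression and need not be confirmed | No; it is not confirmed |
| Controlled at 24 weeks? | Yes, through the PR | No; at most 120 days, below 161 |
| Controlled at 16 weeks? | Yes, through the PR | Depends on how SD duration is measured |

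At 16 weeks, if SD is counted to the PD scan, 106 to 120 days meets the 105-day threshold and the patient qualifies under both documents. If SD is counted to the last scan without progression (about day 57), the patient qualifies only under the SAP. Week 24 is the unambiguous difference.

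**Direction.** Every patient with a confirmed CR or PR also has at least one visit response of CR or PR. Dropping confirmation can therefore add responders but not remove any, so the shift in DCR is upward or nil.

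**Size per reclassified patient**, 100/n:
- n = 26: 3.8 points
- n = 11: 9.1 points
- n = 10: 10.0 points

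**Illustration for an expanded SARCOMA cohort.** All counts are assumed. The mid-P 90% limits are the values of θ at which P(X > x) + ½P(X = x) equals 0.05 (lower) and 0.95 (upper).

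| Patients counted as controlled | DCR at 24 weeks | Mid-P 90% CI |
|---|---|---|
| 5/26 (base) | 19.2% | 8.9% to 34.5% |
| 6/26 (one added) | 23.1% | 11.7% to 38.8% |
| 7/26 (two added) | 26.9% | 14.5% to 43.0% |
| 8/26 (three added) | 30.8% | 17.6% to 47.0% |

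**The case against.** **The missing time condition is not the SAP's doing.** A reader might infer that the SAP, contrary to the protocol, began counting patients who progressed before week 24 as controlled. The documents do not support that as a general statement. Protocol 9.4.1.7 has the same structure: a time threshold for stable disease and none for responders. A confirmed responder who progresses before day 161 counts at 24 weeks under both documents. The SAP's own departure is the loss of confirmation.

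**Not every unconfirmed response counts.** BoR in SAP 3.2.5 stops at progression or subsequent cancer therapy, and 3.2.6 uses data only up to first progression. The point covers responses within those limits.

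**The protocol's DCR section does not itself say confirmed.** That is true of 9.4.1.7, so the conflict has to be read from 9.4.1.6 and 9.5.1.3 together. The sensitivity sentence in 9.5.1.3 also repeats the one in the ORR section and speaks of tumor response. Even so, it stands under the DCR heading, and there unconfirmed response is an additional analysis, not the main one.

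**The consequence is limited.** DCR carries no hypothesis test, threshold or decision rule. Confirmed BoR is tabulated on the FAS and visit responses are listed, so a careful reader could trace the unconfirmed cases. This lowers the stakes but does not remove the contradiction.

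**Conclusion.** The point stands as an undeclared change of definition for a secondary endpoint. SAP 3.2.6 conflicts with SAP 3.2.5, with protocol 9.4.1.6 and 9.4.1.7, and with the sensitivity role in protocol 9.5.1.3. Neither Section 6 nor the SAP's DCR analysis section repairs it.

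The demonstrated effect is at 24 weeks: upward by 3.8, 9.1 or 10 points per affected patient for n = 26, 11 or 10. This assumes a patient with no confirmatory scan between week 8 and progression at week 16. How many such patients there will be cannot be known from the documents. At 16 weeks an effect is possible but not shown, because neither DCR definition says whether SD duration runs to the PD scan or to the last scan without progression.

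A reader might also infer that the primary result is inflated. It is not: ORR is defined on confirmed responses in SAP 3.2.1, and the SARCOMA stopping and rejection rules rest on ORR.

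**What to change.** In SAP 3.2.6, replace unconfirmed with confirmed CR or PR as the main responder component. In SAP 4.2.2.6, add DCR with unconfirmed CR or PR on the evaluable set as a sensitivity analysis. Protocol 9.5.1.3 already provides for it, so it needs no entry as a change. If the sponsor prefers unconfirmed response as the main definition, the alternative is to declare and justify it in Section 6, resolve the clash with 3.2.5, and add a confirmed-response DCR.

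Two clarifications are worth making at the same time:
- State how SD duration is measured, since it decides the 16-week classification.
- Optionally, state whether responders must also be progression-free at 16 or 24 weeks. Neither document requires this now, so adding it would be a change from the protocol and should be listed in Section 6.

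The cost is SAP wording and programming. No new data are needed. Reported DCR may be slightly lower, and the primary ORR analysis does not change.
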